#### Enrollment

Once enrolled, patients will be randomized to one of two groups: one group will receive an incisional wound Prevena (experimental) while the other group will receive the standard dressing (control). Randomization will be divided into 4 strata based on the patient's diabetes and smoking statuses (Diabetic smoker/ diabetic non-smoker/ non-diabetic smoker/ non-diabetic non-smoker). The 4 strata have been computer-generated using a in a 1:1 ratio of Prevena vs standard dressing in each

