# strata. Given the sample size of the study each strata has been generated to include up to 60 patients. A patient is considered enrolled after he/she has been randomized.

# Peri-operative wound management Antibiotic Prophylaxis:

All patients will receive perioperative standard of care intravenous antibiotics at the surgeon's discretion. The antibiotics will be given for 24 hours following surgery.

All patients will be prepped and draped in the normal sterile fashion using Chlorhexidine skin prep.

The incisions will be made using a skin knife. Both groups will undergo approximation of the subcutaneous tissue using 2.0 or 3.0 Vicryl interrupted sutures. For skin closure:

1) The incisions will be re-approximated using skin staples at least 1 cm apart (to allow drainage from the subcutaneous tissue).

OR

2) 2.0/3.0 Nylon interrupted or vertical mattress sutures at least 1 cm apart (to allow drainage from the subcutaneous tissue) will be used.

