# Postoperative wound management

As it will be stated and agreed upon in the informed consent, the dressings in both groups will be removed on post-operative day(POD) # 5-7 (or sooner if redness or signs of infection are noted), by the provider/research coordinator in the clinic or on the ward if they are an inpatient. Then the provider/research coordinator will repeat the swabbing procedure mentioned above. Once swabbing is complete, an NP or a PA who are blinded to the study, will come in and asses the wound for healing, infection and other complications.

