Based on the annual number of open procedures at John Hopkins Medical Institutes the investigators anticipate completing the inclusion of patients within a two-year period. Therefore, we plan to enroll a total of n = 108 patients over two years.

Each eligible patient will have an equal chance of being in either group (Prevena vs. standard dressing) regardless of age or comorbid conditions. However, at 6-month intervals a statistical analysis will compare covariates between the two groups. If there are any statistically significant differences between the Prevena/Non-Prevena groups in numbers of diabetics, smokers or immuno-compromised patients (such as being on steroids) an attempt will be made to equalize the numbers on both sides for the following 6-month period. Once randomized, the participant will undergo the specified procedure and at the conclusion of the case when the incision is closed have either Prevena vs. Standard of Care dressing applied. The dressing will be monitored over a 5 day period where it will then be removed. The participant will be followed thereafter until their sutures/skin staples are removed (Figure 1).

Each participant will be followed though POD 30-35. This time frame for follow up was chosen because:

- a. It will minimize data lost to follow up.
- b. It will maximize the opportunity for detection of infection, since the majority of SSIs are apparent by postoperative day 3-5.
- c. The standard of care at the Johns Hopkins surgical department includes a post-op check and visit 5 to 14 days following surgery.

Participants will be seen on the day of surgery, POD1-2, POD 5-7, POD 12-14, and POD 30±5 for a total of 5 encounters.

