# b. Secondary outcome variables:

- 1. Other wound complications (such as dehiscence, seroma and hematoma)
- 2. Skin bacterial count after treatment

- 3. Wound healing time
- 4. Quality of life scores (SF-36 or VQL)
- c. Statistical plan including sample size justification and interim data analysis.

Power and sample size were calculated using SamplePower 2, alpha set at .05, and power of at least 80%. Current literature values suggest a similar SSI rate of 17-24%.(14, 15)

The use of Prevena has been tested in a small retrospective study (52 Prevena devices) of groin incisions in vascular surgery that yielded a large difference of 24% in SSI rates (Prevena 6%, Non-Prevena 30%).(15) Another retrospective study of Prevena use in plastic surgery showed a difference of 17% in SSI rates in patient groups receiving skin grafts (Prevena 3%, Non-Prevena 20%).(14) However, to this date the use of Prevena has not been documented in obese patients.

For a difference of 24% between control and Prevena groups, 27 patients per group (N=54) are needed to achieve power of 80%. Decreasing the group difference to 20% requires 39 patients per group (N=78) for power of at least 80%. Decreasing the group difference even further to 17% requires 54 patients per group (N=108) for power of at least 80%. To detect a smallest difference of 17%, we estimated the need for a total of 108 patients to be enrolled in this study.

- d. Early stopping rules.
  - 1. Inability to tolerate the Prevena Wound VAC
  - 2. Allergic reaction to the Prevena Wound VAC
  - 3. Evidence of wound infection during the use of Prevena Wound VAC
  - 4. Fever of >38.0 during the time the Prevena Wound VAC is in place (the wound VAC should be removed and infection of the skin ruled out)
  - 5. Statistical evidence that the Prevena Wound VAC has better outcomes versus the standard of care wound dressing\*

\*we will carry out a review of the outcomes every 6 months in this study

In order to alleviate the possibility of diabetes and smoking influencing a patient's wound healing outcomes, we stratified our randomization groups into 4 strata:

- 1) Diabetic Smoker
- 2) Diabetic Non-smoker
- 3) Non-diabetic Smoker
- 4) Non-diabetic non-smoker

Given our sample size we ran the randomization schemes for up to 60 patients in each strata.

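### The 6-monthly rule to equalise diabetics, smokers and immunocompromised patients between arms has no stated mechanism and is not reconciled with the stratified 1:1 lists

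*Combined protocol and SAP*

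**What the plan says.** Under Enrollment in section 1 (Study Procedures), patients are randomised within four strata defined by diabetes and smoking: "The 4 strata have been computer-generated using a in a 1:1 ratio of Prevena vs standard dressing in each" stratum. The extracted text has a gap where the randomisation method would stand, so a block size may exist, and its absence is not held against the plan. The lists are finite: "each strata has been generated to include up to 60 patients". Section 4 (Study Statistics), item d, repeats this ("we ran the randomization schemes for up to 60 patients in each strata") and gives the purpose of stratifying: "In order to alleviate the possibility of diabetes and smoking influencing" wound healing.

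Item b of section 1 states that "Each eligible patient will have an equal chance of being in either group", whatever the comorbidities. The next two sentences qualify this. Covariates are tested between arms every 6 months, and a significant difference in diabetics, smokers or immunocompromised patients means that "an attempt will be made to equalize the numbers on both sides for the following 6-month period". Immunosuppression is recorded before surgery (Consent subsection) but does not define a stratum.

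Two other statements bear on the point. The note to the early stopping rules says "we will carry out a review of the outcomes every 6 months in this study". Wounds are assessed by "an NP or a PA who are blinded to the study".

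**The concern.** If randomisation is sound, any baseline difference between the arms is due to chance, and a significance test of it only shows how unusual that chance result is. A rule that changes allocation or enrolment after such a result reacts to noise. Here it does so by a method that nobody has written down. Two teams could follow the text faithfully, one issuing fresh 1:1 lists with immunosuppression added and the other assigning by running tally, and so run materially different trials.

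Allocation is at stake. Comorbidities are known before randomisation, and no available section separates the 6-monthly reviews from recruitment. If recruiters learned which arm was short of, say, immunocompromised patients, some assignments could be guessed. That is an inference and not something the plan states. Blinded wound assessment protects the outcome but not the choice of whom to enrol.

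**Working it through.** **1. The texts side by side.**
- Diabetes and smoking: the lists already aim at 1:1 within every diabetes-by-smoking cell, so the rule largely duplicates them.
- Immunosuppression: it triggers the rule but is not a stratum. The existing lists cannot be used to balance it, so new lists, a departure from the lists or selective enrolment would be needed. None of these is described.
- Target: the word for numbers refers back to counts of diabetics, smokers and immunocompromised patients. The rule is therefore about covariate counts between arms.

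**2. The plan's own figure.** The point does not depend on the sample size, but the design figure is used for scale. For SSI rates of 20% vs 3%, two-sided alpha 0.05 and 80% power, with mean rate 0.115:

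n = [1.96·√(2·0.115·0.885) + 0.842·√(0.20·0.80 + 0.03·0.97)]² / 0.17² = (0.884 + 0.366)² / 0.0289 = 54.1 per arm.

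The plan states 54, so the figure is reproduced (55 if rounded up). Power at 54 per arm is 79.9% by this formula and 84.5% by exact enumeration of the uncorrected Pearson test.

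**3. How small a difference fires the rule.** 108 patients over two years gives 108/4 = 27 per 6 months, so looks fall at about 27, 54 and 81 patients. At the first look, with arms of 13 and 14, suppose 4 immunocompromised patients are all in the arm of 13. The pooled rate is 4/27 = 0.148, and chi-square = (4/13)² / [0.148·0.852·(1/13 + 1/14)] = 5.06, p = 0.024. A 4-0 split is enough.

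**4. How often it fires by chance.** The documents give no prevalences, test or block size. Assumed: three independent covariates with prevalences (diabetes, smoking, immunosuppression) of A = 30/20/10%, B = 25/15/5% and C = 40/20/10%; two-sided 0.05; looks at 27, 54 and 81. Simulated 20,000 times per cell for Pearson and 8,000 for Fisher.

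| Lists within strata | Pearson A / B / C | Diabetes or smoking fires (Pearson) | Fisher A / B / C |
|---|---|---|---|
| Blocks of 4 | 8.8 / 5.2 / 9.2% | 0.00-0.03% | 4.4 / 1.6 / 4.3% |
| Blocks of 6 | 9.1 / 5.9 / 8.8% | 0.24-0.40% | 4.3 / 2.1 / 4.7% |
| One 60-long list | 21.3 / 17.6 / 21.1% | 13.0-13.6% | 11.6 / 9.2 / 11.6% |

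Independent reruns of the Pearson rates for blocks of 4 and 60-long lists agree to within about one point. With small blocks nearly all firing comes from immunosuppression, the covariate that the lists do not cover.

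**5. What it could do.** If equalising meant deterministic assignment by tally, the tally would set the arm of 0.08-0.25 of 108 patients per trial on average with blocks of 4, and 0.71-1.13 with 60-long lists. With fresh 1:1 lists it would set none.

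A pessimistic model then lets recruiters guess every such assignment, halve the SSI odds of patients sent to Prevena and double those of patients sent to control (null rate 20%, each covariate odds ratio 2, 60,000 trials per cell):
- In trials where the rule fires, the SSI difference shifts by 0.39-0.70 points (blocks of 4) or 1.04-1.30 points (60-long lists).
- Over all trials it shifts by 0.02-0.06 or 0.19-0.27 points, against a design difference of 17.
- Pearson type I error rises at most from 4.77% to 4.85%.

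**The case against.** The strongest reply is that the plan promises only an attempt, and that fresh 1:1 lists with immunosuppression added would satisfy the wording. Every patient would then keep the equal chance that item b promises. This stands. A reader might infer that the rule flatly contradicts the lists, breaks 1:1 allocation or abandons randomisation. The text supports none of these. It supports only an unspecified mechanism that is not reconciled with lists already made.

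It can also be said that covariate-adaptive allocation is a legitimate family of designs, and that this rule is the only balancing provision that immunosuppression has. That stands too. The fault is not that immunosuppression is named but that no method is given, and deleting the rule gives up the provision.

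Finally, the harm needs a chain of events that no section documents: tally assignment, recruiters knowing which arm is short, correct guessing, and strong selection on SSI risk. A reader might infer selection bias or an inflated type I error from the shared 6-month interval for covariate and outcome reviews. The documents do not say that those who review also recruit, and the modelled effect is small even if all of this is granted.

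The reply does not remove the core of the point. The rule is still triggered by chance differences, and for immunosuppression it can be carried out only by replacing or departing from the lists or by enrolling selectively.

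**Conclusion.** The point holds as a low-priority correction. The missing mechanism and the lack of reconciliation with the stratified lists are plain from the text. The firing rates (about 5-9% with blocks of 4, about 17-21% with 60-long lists, lower with Fisher tests) rest on assumed prevalences, look times, test and block size. The bias figure, at most 0.3 points averaged over all trials, rests in addition on deliberately pessimistic assumptions about recruiters. Whether allocation would become predictable cannot be told from the documents. The case for change is that the rule responds to chance by an undefined route, duplicates the stratification for two of its three covariates, and costs almost nothing to remove.

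**What to change.** Delete the two sentences in section 1, item b, on 6-monthly covariate testing and equalising. Keep the stratified 1:1 lists for the whole trial. State that the primary SSI outcome is analysed by the four randomisation strata, for example by Cochran-Mantel-Haenszel (CMH) with a stratified risk difference. Report immunosuppression by arm, with at most a sensitivity adjustment. If the sponsor wants active balance on immunosuppression, it should instead prespecify a concealed method that keeps a random element, such as an added stratum or minimisation, with matching adjustment in the analysis.

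Costs:
- **Patients and visits:** none extra.
- **Power:** at 20% vs 3%, simulated power is 84-85% with Pearson and 83-86% with CMH, less than 1 point apart in every scenario run.
- **List length:** a stratum may pass 60, so say that its list is extended by the same method. The non-diabetic non-smoker stratum expects 108·0.70·0.80 = 60 (A), 108·0.75·0.85 = 69 (B) or 108·0.60·0.80 = 52 (C) patients under the assumed prevalences.
- **Immunosuppression:** with deletion alone, a chance imbalance is handled only by a thin adjustment. Expected SSIs are 54·0.20 + 54·0.03 = 12.4. Treatment, three stratum terms and immunosuppression make 5 parameters, so 12.4/5 = 2.5 events each. At 10% prevalence only about 2 SSIs are expected in immunosuppressed patients.

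### Allocation is generated before surgery but not needed until after skin closure and swabbing, and nothing withholds it from the surgical team in between; open it after closure instead.

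*Combined protocol and SAP*

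**What the plan says.** **Order of events.** Under Study Procedures, Enrollment: "Once enrolled, patients will be randomized to one of two groups". The text that follows adds: "A patient is considered enrolled after he/she has been randomized". The paragraph on study duration (item b) puts this before the operation: "Once randomized, the participant will undergo the specified procedure and at the conclusion of the case when the incision is closed", the Prevena or standard dressing is applied. The Swabbing section uses the allocation for the first time only after the skin has been closed and the incision swabbed.

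**Choices in the interval.** Under Peri-operative wound management: "All patients will receive perioperative standard of care intravenous antibiotics at the surgeon's discretion", and "The antibiotics will be given for 24 hours following surgery". For the skin there are two options joined by OR: "The incisions will be re-approximated using skin staples at least 1 cm apart", or "2.0/3.0 Nylon interrupted or vertical mattress sutures at least 1 cm apart". No rule says which to use, and the person who chooses is not named.

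**Blinding.** Item c of Study Procedures calls the trial single blinded and justifies this by participants' possible bias. The postoperative and follow-up sections blind the nurse practitioner or physician assistant who assesses the wound. The operating team is not mentioned.

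**The concern.** The arms are meant to differ only in the dressing, which goes on last. Generating the arm earlier opens a period in which other care relevant to SSI is still being decided. If the team knew the arm, it could lean towards one closure or one antibiotic in one group without intending to. The protocol itself records a favourable prior view of Prevena at the institution.

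A blinded assessor cannot undo a difference in care already delivered. Stratification covers only diabetes and smoking, and no analysis adjusting for closure or antibiotic is planned, so an imbalance would be read as a dressing effect on the primary outcome. The closing swab falls in the same interval.

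Separately, a patient whose operation is cancelled, or whose incision is not closed as planned, is already randomised and enrolled. That patient uses up one of the 108 places for a reason unrelated to either dressing.

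**Working it through.** **1. The plan's own figure.** Study Statistics, item c: a 17-point difference (20% v 3%), alpha 0.05, power at least 80%, 54 per group. Sidedness is not stated; two-sided is assumed. With pooled variance under the null and no continuity correction, the mean risk is (0.20 + 0.03)/2 = 0.115 and

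n = [1.960·√(2·0.115·0.885) + 0.842·√(0.20·0.80 + 0.03·0.97)]² / 0.17² ≈ 54.1 per arm.

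This rounds up to 55, against the stated 54; power at 54 is 79.9%. The figure reproduces closely. The timing of allocation does not change it, but no dropout allowance is stated, so there is no slack for patients lost before the dressing is applied.

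**2. The interval, from the text.**

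| Step | Allocation needed? | Discretion left open |
|---|---|---|
| Enrolment and randomisation | No | – |
| Antibiotics | No | Agent, within standard of care |
| Skin prep, subcutaneous closure | No | Prep agent and suture type common to both arms |
| Skin closure | No | Staples or nylon, no rule |
| Closing swab | No | Technique prescribed |
| Dressing | **Yes** | – |

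Nothing before the last row requires the arm to be known.

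**3. How large could a bias be? Illustration only.** None of these inputs is in the documents, except that 20% is the control rate behind the 17-point target.

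- Control SSI 20%; the dressing has no effect; 54 per arm.
- Half of controls receive the higher-risk option, with relative risk RR = 1.5 or 2.0 against the other.
- The share in the Prevena arm is lower by s = 10, 20 or 30 points.
- Test: uncorrected Pearson chi-square, two-sided 5%. The plan names no test for the primary outcome.

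Risk under the lower-risk option: r₀ = 0.20 / [1 + 0.5(RR − 1)], which is 0.20/1.25 = 0.160 for RR 1.5 and 0.20/1.5 = 0.1333 for RR 2.0.

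Prevena risk: r₀·[1 + (0.5 − s)(RR − 1)]. For example, RR 1.5 and s = 0.10 give 0.160 × 1.20 = 19.2%; RR 2.0 and s = 0.30 give 0.1333 × 1.20 = 16.0%.

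Type I error is the sum of the two binomial probabilities over all pairs of event counts at which the test rejects.

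| RR | Shift s | Prevena SSI | Spurious difference | Two-sided rejection |
|---|---|---|---|---|
| – | 0 | 20.0% | 0 | 5.1% |
| 1.5 | 10 | 19.2% | 0.8 points | 5.2% |
| 1.5 | 20 | 18.4% | 1.6 points | 5.6% |
| 1.5 | 30 | 17.6% | 2.4 points | 6.2% |
| 2.0 | 10 | 18.7% | 1.3 points | 5.4% |
| 2.0 | 20 | 17.3% | 2.7 points | 6.5% |
| 2.0 | 30 | 16.0% | 4.0 points | 8.4% |

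Most of the rejections favour Prevena: the chance of a false win rises from 2.5% to between 3.2% and 7.8%.

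**4. A second set of assumptions.** Let a protective measure be used in an extra share x of the Prevena arm, so that Prevena risk = control risk × [1 − x(1 − RR)]. With control SSI 17% to 24%, x from 10% to 50% and RR 0.5 to 0.7, the spurious difference runs from 0.17 × 0.1 × 0.3 = 0.5 points to 0.24 × 0.5 × 0.5 = 6 points. By normal approximation the false-win chance is 2.9% to 11.6%, against a nominal 2.5%. An imbalance in the other direction would hide a real benefit by a similar amount.

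**The case against.** **Knowledge of the arm.** A reader might infer that the surgeon knows the arm while choosing antibiotics and closure. The documents do not say so. They do not say who holds the list or when it is opened, and they first act on it after the swab. What stands is narrower: no step prevents that knowledge.

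**Little room for bias.** Chlorhexidine prep, subcutaneous closure, minimum stitch or staple spacing and the 24-hour antibiotic period are common to both arms, and antibiotics must be standard of care. This is correct. It limits the bias but leaves the antibiotic agent and the closure method open.

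**Assumed size.** Nothing in the documents shows that staples against nylon, or one standard antibiotic against another, changes SSI risk. The lowest case is negligible, the highest needs RR 2.0 and a 30-point shift together, and even 4.0 points is small beside the 17-point target. All of this stands; the figures show scale and are not evidence of harm.

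**The closing swab.** One might call it the baseline for Aim 2. The documents never do; Aim 2 compares counts at dressing removal, and the swab technique is prescribed. The swab matters here only as one more step that could be done knowing the arm.

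**Losses before closure.** Surgery is elective and no cancellation rate is given, so these losses cannot be quantified.

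**Partial remedy.** Opening the allocation at closure cannot protect antibiotic decisions made afterwards, which is why recording by arm is also needed.

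**Conclusion.** The point holds as an inexpensive improvement to a stated sequence. Randomisation precedes surgery, the allocation is not needed until after closure and swabbing, and no provision keeps it from the surgical team while antibiotic agent and skin closure are still open. That leaves an avoidable route to performance bias in the primary comparison and avoidable losses after randomisation.

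The documents do not support the stronger conclusion that the SSI comparison will be biased. Whether the team knows the arm, whether the choices would shift, in which direction, and whether they affect SSI are all unknown. The 0.8 to 4.0 points and the 5.2% to 8.4% type I error depend wholly on the assumptions listed. The sample size of 108 is unaffected.

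**What to change.** In the Enrollment section, the enrolment definition that follows it and the study-duration paragraph, state that:

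1. consent and the diabetes/smoking stratum are recorded before surgery;
2. the next allocation in that stratum is opened in the operating room only after skin closure and the closing swab, and is withheld from the surgical team until then;
3. the patient counts as randomised and enrolled at that point.

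Also record the skin closure method and the antibiotics given (agent and duration), and report them by arm. This shows whether care differed, including after closure, where later opening gives no protection.

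The cost is protocol wording, someone to release the allocation at closure at both hospitals, a Prevena device on hand for every case, and two recorded items per patient. No extra patients, visits or procedures are needed, and no clinical option changes.
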